2.1 STUDY DESIGN

Observational, retrospective, multicentre study in spanish patients with metastatic Renal Cell Carcinoma (mRCC) treated with sunitinib as a first-line treatment (treatment with previous cytokine therapy is accepted) according to clinical practice who obtained a complete response (CR) to treatment in one of these 2 situations:

- a) Complete response (CR) obtained exclusively with first-line sunitinib treatment (sunitinib CR).*
- b) Response obtained after a period of time on treatment with sunitinib in which local treatment was also performed (surgery of the residual metastasis/metastases, radiofrequency ablation or radiotherapy) to achieve the total macroscopic disappearance of the disease, according to the opinion of the physician responsible for the patient (CR + local treatment).*

The patient population eligible for this study includes any patient with advanced or metastatic renal cancer treated with Sunitinib and who has achieved a CR to the tumour and its metastases at some point in the treatment and according to the usual evaluation criteria in daily clinical practice irrespective of whether it was obtained with Sunitinib alone or local treatment was required to eradicate all lesions: (residual metastasis(es), radiofrequency ablation or radiotherapy)

The requirements for a patient's inclusion are that:

- 1. These patients must have Sunitinib as first-line treatment in accordance with its Summary of Product Characteristics.*
- 2. Collection of clinical, safety and response data in patients with advanced kidney cancer.*

The study is expected to be conducted in at least 50 sites throughout Spain in order to reach the maximum number of study patients.

Case collection will start at each site after the contract with the site has been signed, all the study documentation is available and training in the procedures and objectives of the protocol has been provided by the person appointed by the sponsor.

Any number of patients that meet the inclusion criteria and no exclusion criteria may be recruited at the site.

This is an observational study designed to reflect routine clinical practice; there will be no interference with the daily routine of the medical care provided to kidney cancer patients.

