4.1.1. Inclusion Criteria

Patients must meet all the inclusion criteria below to be eligible for inclusion in the study:

[figure not shown]
1. Patients aged 18 years or older who have been treated for a metastatic renal carcinoma with first-line sunitinib in (prior cytokine treatment is admitted) between 2007 and October 30, 2018 and have obtained, as best response to treatment, total disease remission in the opinion of the treating physician from the clinical, radiological and/or macroscopic standpoint. This response must have been achieved through two possible strategies:
 - a. Systemic treatment with Sunitinib alone.
 - b. Treatment with Sunitinib and subsequent local treatment for one or several residual lesions that have not responded to the drug (traditional surgery, radiotherapy, SBRT (Stereotactic Body Radiation Therapy)).
2. The duration of the CR must have been confirmed by at least 2 consecutive imaging tests with no limit on the duration of this response. Patients with subsequent progression may be included in this registry.
3. Patients of any risk group.
4. Tumours of any histology.

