5 OBJECTIVES AND VARIABLES

The primary objective of the study is *to identify patients with metastatic renal cell carcinoma (mRCC) who obtained a complete response (CR) to treatment with Sunitinib exclusively or with Sunitinib and a local treatment to eliminate residual disease in the opinion of the clinician. Complete response (CR) is defined as the disappearance of all measurable lesions according to the investigator's criterion in at least 2 consecutive CT scans.*

The clinical baseline characteristics of these patients and the tumour will be described in order to look for predictive response factors.

[figure not shown]
The intention is to describe the therapeutic strategy used in patients who obtained the greatest clinical benefit in the cases described once the macroscopic lesions were eradicated in order to draft recommendations to be followed once the registry's statistical analysis is available.

The variables to be analysed for this study will be obtained from the patients' medical records and case report forms according to the protocol. The data will be recorded on the paper CRF designed for this study where the following patient information will be included:

DEMOGRAPHIC AND DISEASE INFORMATION

- 1) Age at the start of treatment for metastatic disease
- 2) Functional status, measured by the ECOG scale (0, 1, 2, 3, 4) and/or by means of the KPS (Karnofsky Performance Status) scale, at the start of treatment (see annex I)
- 3) Motzer and Heng prognostic criteria
- 4) Laboratory data (haemoglobin, leukocytes, corrected calcium, LDH levels, lymphocytes, platelets, neutrophils, lymphocytes)
- 5) Comorbidities
- 6) Date the disease was diagnosed
- 7) Metastasis site(s) and number
- 8) Furhrman grade (I, II, III, IV)

PFIZER CONFIDENTIAL

- 9) Tumour stage (TNM)
- 10) Previous nephrectomy
- 11) Necrosis

TREATMENT

- 1) Start date of treatment with first-line Sunitinib
- 2) Initial dose and treatment regimen
- 3) Type of treatment received (monotherapy or in combination with local treatment) and technique used in the case of local treatment
- 4) Response to treatment.
- 5) Date of completion of the treatment after CR if treatment is interrupted
- 6) Modification of dosage and/or treatment regimen, number of changes in the dose, reason, date and new dose
- 7) Dose interruptions, number of interruptions, reason, date of interruption and restart and new dose

CCI

- 9) Adverse reactions

POST-TREATMENT

- 1) Continuation of treatment in 1st line

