- 2) End date and reason
- 3) Date of progression
- 4) Date of and reason for death
- 5) Post-Sunitinib treatments (another TKI, mTOR, immunotherapy)

The following aspects will be assessed using the variables collected:

- **Time from nephrectomy to the start of systemic treatment:** defined as the time interval from the day of the nephrectomy to the day treatment with Sunitinib started.
- **Time to CR:** defined as the time interval from the day treatment with Sunitinib started until the day the complete response is documented in the first CT scan without lesions.
- **Duration of treatment with Sunitinib once CR is reached:** defined as the time interval from the day on which the complete response is documented until the day that the definitive discontinuation of the treatment is confirmed, either at the patient's own decision or at the doctor's decision.
- **Time to progression (TTP):** defined as the time interval from the day on which the complete response is documented until the first day that objective tumour progression, if any, is observed.
- **Time to change of treatment:** in patients who continue treatment with Sunitinib once the lesions have disappeared, it is defined as the time interval from the day on which the complete response is documented until the first day on which the change of treatment due to unacceptable toxicity is documented, as applicable.
- **Time to death:** defined as the time interval from the day on which the

Pfizer Confidential

complete response is documented to the day on which death from any cause is documented, if it occurs.

- **Duration of complete response (DOR):** defined as the time interval from the date on which the complete response to Sunitinib is identified until the date of the CT scan conforming tumour progression, the change of treatment due to unacceptable toxicity, death from any cause or until the date of the last follow-up at the close of the study. It represents the time that the patient survives without signs of disease.

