- Time on treatment with Sunitinib until complete remission of lesions, calculated as the difference between treatment start date and CR confirmation date (2nd CT scan).
- Duration of complete remission (DOR)
- Progression-free survival (PFS) or time from remission to disease progression, change of treatment due to unacceptable toxicity or death. It will be calculated as the time elapsed from the RC confirmation date (2nd CT scan) until the date of progression/death or change of treatment for unacceptable toxicity, as applicable, or else it will be censored on the date of the last patient follow-up.

Taking into account the asymmetry normally observed in the distribution of survival times and that follow-up periods may be uneven (different study entry date), the Kaplan-Meier method will be used to estimate the median time to CR together with its 95% confidence interval. The median will indicate when complete remission of the disease occurred in 50% of patients.

In order to find associations between time to CR and the baseline features of both patient and tumour, a log-rank test will be used for comparison between groups and the determination of the statistical significance of the correlation between each of the baseline variables and the time to complete remission of disease. The following baseline characteristics are considered:

[figure not shown]
- Demographic characteristics
- Comorbidities
- Tumour data
- Prior nephrectomy in the treatment of metastatic renal cancer
- Classification of the risk group according to Motzer and/or Heng criteria.
- Patient's baseline status, including ECOG grade, presence of anaemia, corrected calcium, LDH levels, neutrophil and platelet levels.

This analysis will establish which baseline characteristics are associated with a shorter complete response time to treatment.

As part of the secondary objectives, the doses and treatment regimens observed in the sample will also be descriptively summarised by means of absolute and relative frequencies. In the case of changes in the treatment dose, the frequency of patients with dose increase, dose reduction and changes in the rest regimen will be specified. Similarly, the most frequent reasons for changes in dosage and/or treatment regimen to RC will be reported.

Frequencies of the type of treatment received will be presented, depending on whether it

Pfizer Confidential

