is monotherapy or combination with a local treatment for one or several residual lesions. In the group of patients who received local treatment, the frequency distribution of the techniques used (traditional surgery, radiotherapy and SBRT) will be presented, at the time they are applied, as well as histology, degree of tumour necrosis and the surgical complications reported.

In the sub-sample of patients who discontinue systemic treatment after a period of treatment with maintenance of CR, the most frequent reasons for the decision and the frequency of cases in which the patient was consulted in the decision to discontinue treatment will be reported, and the cases in which it was at the patient's or the investigator's request.

The distribution of frequencies of the pharmacological group by mechanism of action used in patients in the second-line treatment after disease progression will be reported.

Once the descriptive statistics have been presented, and provided that the proportional *hazards* assumption or relative risk of the covariates of interest (patient and tumour baseline conditions, dose and treatment regimen and type of treatment received) are fulfilled, a multivariate Cox regression will be performed to investigate the effect of all prognostic factors on CR/PFS. The *hazards ratio* (HR) will be estimated, along with their 95% confidence intervals, as parameters of association between each one of the predictive factors of response and the time to complete remission or disease progression.

This information will make it possible to produce recommendations for the therapeutic strategy to be followed in patients who obtain complete remission of the macroscopic lesions to the treatment with Sunitinib.

For the safety analysis of treatment with Sunitinib, the percentage of patients who have presented serious and non-serious adverse events explicitly attributed to Sunitinib during treatment will be presented by means of descriptive tables. The frequency of adverse events recorded will be reported based on severity, the highest grade and whether it or they led to a dose interruption or modification.

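### The pooled Cox covariate list puts type of treatment received, settled only after sunitinib starts, into the time-to-CR model, so a null or beneficial effect of local treatment is biased downwards (immortal time)

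*SAP*

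**What the plan says.** SAP 7.2.4 makes the multivariate Cox regression conditional on proportional hazards for the "covariates of interest (patient and tumour baseline conditions, dose and treatment regimen and type of treatment received". HRs with 95% confidence intervals are to be reported "as parameters of association between each one of the predictive factors of response and the time to complete remission or disease progression". One list serves both outcomes. SAP 7.2.2 gives the levels of type of treatment as sunitinib monotherapy and sunitinib with later local treatment.

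Time to CR starts at sunitinib start wherever it is defined. SAP 5 has the "time interval from the day treatment with Sunitinib started until the day the complete response is documented", and SAP 7.2.4 has it "calculated as the difference between treatment start date and CR confirmation date (2nd CT scan". The two end on different scans, but the origin is the same, and the origin is what matters here. PFS in SAP 7.2.4 starts at CR confirmation.

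On the timing of local treatment, SAP 4.1.1 describes the second route to CR as "Treatment with Sunitinib and subsequent local treatment for one or several residual lesions that have not responded to the drug". SAP 2.1 describes group (b) as "Response obtained after a period of time on treatment with sunitinib in which local treatment was also performed".

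SAP 5 collects "Initial dose and treatment regimen" and, separately, later changes of dose or regimen. The Cox list does not say which of these is meant. No time-dependent coding, landmark or outcome-specific covariate list is stated.

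**The concern.** A covariate in a time-to-event model should be known when the clock starts. Here, whether a patient belongs to the local-treatment group is settled months later, and only if CR has not yet occurred on the drug. All the waiting time before the procedure is event-free by definition, yet an ordinary covariate counts it as time at risk under local treatment. Patients with early CR on the drug can fall only in the other group. Since CR is the favourable event, both features lower the HR for local treatment.

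The HR would be printed with a confidence interval and read against the p<0.05 threshold of SAP 3.2. A procedure that speeds remission could be reported as having no association with it, or as going with slower remission. Dose and regimen raise the same question if later changes enter the time-to-CR model.

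**Working it through.** The plan gives no HR, power or event count for this model, so there is no figure to reproduce.

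**1. Timing.** Time to CR: origin at sunitinib start, group settled later, so the covariate is not known at time zero. PFS: origin at confirmed CR, group already settled, so this bias does not arise. The log-rank comparisons of time to CR in SAP 7.2.4 list baseline features only and are also unaffected.

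**2. Direction, by hand.** Let drug-induced CR have constant hazard λ and the procedure hazard fλ. A patient is in the local group if the procedure time L comes before the drug-CR time T. After the procedure the CR hazard becomes θλ. Everyone reaches CR, as the registry requires.
- Mean time to CR, drug alone: 1/[λ(1+f)].
- Mean time to CR, local group: 1/[λ(1+f)] + 1/(θλ).
- Ratio of event rates, local to drug alone: θ/(θ+1+f), which is always below θ.

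The cited series in SAP 2 has 36 drug-alone and 28 local-treatment cases, so f = 28/36 = 0.778. For θ = 1 the ratio is 1/2.778 = 0.36. For θ = 2 it is 2/3.778 = 0.53. For θ = 3 it is 3/4.778 = 0.63. Simulated Cox HRs at n = 90 in this exponential setting (about 44% local) were 0.30, 0.47 and 0.59. This shows direction only, because exponential times do not fit the cited medians.

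**3. Size, calibrated.** T and L are independent and the group is local if L < T. Three parameters are solved so that P(L < T) = 28/64, the drug-alone median is 12.6 months and the local-group median is 18.5 months (SAP 2). The spread of L is not in the documents and must be assumed. A univariable Cox model is fitted without censoring. A true effect multiplies the hazard of T by 2 after L. The cited ranges, 2-28 months (drug alone) and 5-45 months (local), then show which spreads are plausible.

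| Assumed procedure times | HR, no true effect | HR, true doubling | Typical range, 28 local patients (months) |
|---|---|---|---|
| Lognormal, log-SD 0.3 | 0.25 | 0.40 | 11-32 |
| Lognormal, log-SD 0.5 | 0.35 | 0.57 | 10-37 |
| Lognormal, log-SD 0.8 | 0.44 | 0.71 | 8-44 |
| Lognormal, log-SD 1.0 | 0.48 | 0.79 | 7-49 |
| Nearest the cited ranges | 0.54-0.56 | 0.88-0.91 | 5-38 (Weibull, shape 1) |

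With log-SD 0.3 to 0.5, a local-group minimum of 5 months or less occurs in at most 0.2% of samples of 28. In the lognormal settings shown, a drug-alone minimum of 2 months or less occurs in at most 0.5% of samples. Weibull procedure times of shape 1 give 2-32 months for drug alone and 5-38 for local treatment, with a no-effect HR of 0.54.

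In the nearest settings at n = 90, a true doubling is significantly faster in under 1% of runs and significantly slower in 7 to 9%. I re-ran the calibration and obtained the same HRs to within 0.01.

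**4. Proportional-hazards condition.** With no true effect, in the four lognormal settings, a test at p<0.05 rejected proportional hazards in 23 to 45% of n = 90 runs. Between 55 and 73% of runs passed it and still gave p<0.05 for local treatment.

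**5. Time-dependent coding.** With no selection it recovers the truth (2.02 for a true 2 at n = 90). Among CR patients only, with competing progression, a true 2 becomes about 1.6, or 1.25 to 1.33 with a 30-month window. If instead the procedure itself produces CR and the scan records it 1, 2 or 3 months later, the time-dependent HR is 14-30, 6-14 or 4-9 (log-SD 0.3 to 0.8). It then mostly measures the scan lag.

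**The case against.** The strongest reply is that the SAP never says the covariate is fixed, nor which covariates go with which outcome. The list is pooled and sits inside a proportional-hazards condition, and the log-rank paragraph specific to time to CR names baseline features only. No hypothesis is set (SAP 3.1), and the HRs are called measures of association. This stands as far as it goes: entry as an ordinary covariate is the natural reading, not an explicit statement. But an unqualified covariate is normally entered as fixed, the outcome is named, and step 4 shows that the condition is no safeguard.

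A reader might go further in three ways that the documents do not support.
- That the HR falls below the truth whatever local treatment does. With CR-only selection and competing progression, an assumed strongly harmful effect (true HR 0.2) gave a fixed-covariate HR of 0.27 to 0.52, above the truth. The downward direction holds for a null or beneficial effect.
- That a real doubling would usually appear as significantly slower remission. That comes from tightly clustered procedure times (99% and 77% of runs at log-SD 0.3 and 0.5), which the cited ranges contradict.
- That the registry's recommendations would rest on this HR. SAP 7.2.4 does say "This information will make it possible to produce recommendations for the therapeutic strategy to be followed", but for patients already in CR. PFS from confirmed CR is the more relevant model there, and it is free of this bias.

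The calibrated models also let local-group patients reach CR at their drug-CR time, whereas in the registry the procedure is part of reaching CR. A version with CR recorded a fixed lag after the procedure gave fixed-covariate HRs of 0.37 to 0.68, so the size remains uncertain.

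**Conclusion.** The concern holds for the time-to-CR model only. Followed on its natural reading, SAP 7.2.4 yields an HR for local treatment that carries immortal-time bias, downwards if local treatment has no effect or helps. In the settings nearest the cited ranges, no effect appears as an HR of about 0.54 to 0.56 and a true doubling as about 0.9, with almost no chance of showing as significantly faster. Less dispersed procedure times give 0.25 to 0.48 but fit those ranges poorly.

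These sizes are illustrative. They rest on assumed procedure times, on independence of T and L, and on one cited series that mixes 59 sunitinib and 5 sorafenib patients. The cited medians alone imply a crude HR of 12.6/18.5 = 0.68 under exponential curves, and such data cannot show how much of that is bias. The case for changing the plan rests on the timing of the covariate, not on a particular size.

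**What to change.** In SAP 7.2.4, give each Cox model its own covariate list.
- **Time to CR:** only covariates known at sunitinib start, namely patient and tumour baseline characteristics and the initial dose and regimen. Remove type of treatment received. Describe time to CR separately by route (sunitinib alone; sunitinib plus local treatment), without an HR between routes.
- **PFS from confirmed CR:** type of treatment received may stay. Limit dose and regimen to what is known at CR confirmation.

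Do not substitute time-dependent coding in the time-to-CR model. It removes the immortal time, but the procedure is part of how group (b) reaches CR and the sample is selected on CR, so the resulting HR would still not be interpretable.

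The cost is SAP wording only, since initial dose and regimen are already collected. What is lost is an adjusted HR for local treatment on time to CR, which these data cannot validly give.

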STUDY TITLE:

REGISTRY OF COMPLETE RESPONSES TO SUNITINIB IN SPANISH PATIENTS WITH METASTATIC RENAL CELL CARCINOMA (ATILA STUDY)

PROTOCOL CODE: A6181227

COORDINATING INVESTIGATOR:

The scientific coordinator will be responsible for maintaining the methodological rigour of the study, both in the design phase and in the evaluation of results and writing of the final report. He/she will guarantee the ethical conduct of the study, maintaining the scientific support for all participating doctors until the publication of the study results:

[name]
PPD [REDACTED]
[REDACTED]
[REDACTED]

STUDY SITES:

It is initially considered optimal to include patients in the Medical Oncology Departments of approximately fifty Spanish sites (see “investigators list”).

IEC ASSESSING THE STUDY

PFIZER CONFIDENTIAL

This protocol has been evaluated in the PPD
, Spain.

PRIMARY STUDY OBJECTIVES:

To describe complete responses in daily clinical practice in Spain between June 2007 - 30 October 2018, such as: the documented disappearance of all lesions of metastatic renal cell carcinoma according to the investigator's criteria in at least 2 consecutive CT scans.

To look for associations between CR from a macroscopic point of view and the baseline characteristics of both the patient and the tumour, such as:

- Demographic data (age at the start of treatment)
- Previous nephrectomy
- Classification of the risk group according to Motzer and/or Heng criteria and the association between each prognostic variable, such as: baseline patient status, time from nephrectomy to systemic treatment start, presence of anaemia, corrected calcium, LDH (Lactate Dehydrogenase) levels, neutrophil levels and platelet levels.
- Tumour data: histology, Fuhrman grade, presence of tumour necrosis and number and location of metastases (organs involved).

DESIGN

Post-authorisation, observational, retrospective, multicentre study.

STUDY CONDITION

Advanced/metastatic renal cell carcinoma

STUDY POPULATION AND TOTAL NUMBER OF SUBJECTS

Patients over 18 year-old with advanced carcinoma with a renal cell component who have received sunitinib as a first-line treatment according to drug indication and who have achieved CR according to the responsible medical team criteria, will be included.

During the study recruitment period, the participating sites may include all patients who fulfil the inclusion criteria and none of the exclusion criteria of the protocol.

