8.5. Sample size

Since this is a case registry with descriptive intent, it is not necessary to make a sample size calculation.

It is planned to include around 90 patients according to an initial estimation, but there is no limit of patients to be included as long as they are circumscribed to the period of case collection. There is no predetermined hypothesis with a defined sample.

The period of case collection will be from the approval of the reference Independent Ethics Committee and opening of the centres until July 31, 2019 or the inclusion in the CRF of all localized cases, whichever occurs first.

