The data collected will correspond to those usually collected in the medical record; patient demographic variables (never personal data that could lead the patient to be identified), age at start of treatment, routine laboratory values required in the diagnosis and control of this pathology, patient functional status and clinical status. Treatment compliance, tolerability and adverse events and treatment effectiveness will be collected.

Since this is an observational study, no additional material not provided for in routine practice will be required.

Any patient who meets the inclusion criteria and who does not meet any of the exclusion criteria and has received treatment with Sunitinib prior to participation in the registry will be considered evaluable.

No patient follow-up period is established and nor is there any interview with them, since there is only one moment in which the patient's data are reviewed; this will be when the investigator completes the case report form.

Analysis population

Patients above the age of 18 years with advanced carcinoma with a renal cell component who have received Sunitinib as a first line of treatment according to the indication of the drug and who have achieved a CR according to the criteria of the responsible medical team will be included.

During the study recruitment period, the participating sites may include all patients who meet the study's inclusion criteria and do not meet any of the exclusion criteria.

Since this is an observational and exploratory study, no hypothesis has been established and the number of subjects included will not be pre-established, although a sample of close to 90 cases is estimated in around 50 Spanish sites.

Treatment with Sunitinib will have begun before the patient is included in this registry, hence the treatment decision will depend solely on the treating physician's clinical criteria.

[figure not shown]

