3.2 STATISTICAL DECISION RULES

The statistical significance value is set to $p<0.05$. The SAS statistical software version 9.3 or later (SAS Institute Inc., Cary, NC, USA) will be used.

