4 ANALYSIS POPULATION

4.1 FULL ANALYSIS SET

Since it is an observational and exploratory study, the number of subjects included will not be pre-determined, although a sample of close to 90 cases is envisaged in about 50 Spanish sites; taking the case collection period into account.

Any number of patients that meet the inclusion criteria and no exclusion criteria may be recruited at the site.

Any patient who meets the inclusion criteria and who does not meet any of the exclusion criteria and has received treatment with Sunitinib prior to participation in the registry will be considered evaluable.

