4.1.2. Exclusion Criteria

Patients who meet any of the following criteria will not be included in the study:

1. Patients treated with another drug other than Sunitinib.
2. Patients without radiology reports that substantiate the CR.

PFIZER CONFIDENTIAL

3. Patients without a record of the dose and regimen of Sunitinib.
4. Patients who achieved complete remission after October 30, 2018.

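### Time to CR is cut off by the 30 October 2018 entry limit, but no time-to-CR analysis accounts for sunitinib start date, so factors commoner among late starters are biased toward faster CR

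*SAP*

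**What the plan says.** Inclusion depends on having had a CR: SAP 2.1 states that patients "who have achieved a CR according to the criteria of the responsible medical team will be included". SAP 4.1.2 (and Protocol 8.2.2) excludes "Patients who achieved complete remission after October 30, 2018". The Protocol abstract gives the calendar window: "To describe complete responses in daily clinical practice in Spain between June 2007 - 30 October 2018". About 90 cases are expected (SAP 4.1: "a sample of close to 90 cases is envisaged in about 50 Spanish sites").

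SAP 7.2.4 plans two comparative analyses of time to CR:

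- **Log-rank tests**, one baseline characteristic at a time: demographics, comorbidities, tumour data, prior nephrectomy, Motzer/Heng group, and performance and laboratory status.
- **A multivariate Cox model** for CR/PFS, with "covariates of interest (patient and tumour baseline conditions, dose and treatment regimen and type of treatment received)" as covariates.

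SAP 5 lists "Start date of treatment with first-line Sunitinib" among the data collected. Neither that date nor any calendar period appears in the log-rank list, the Cox covariates or the covariate table in SAP 5.4. SAP 4.4 (subgroups) is marked not applicable. Protocol 8.7 permits a stratified analysis but names no stratum. SAP 7.2.4 mentions uneven entry dates only as a reason to use Kaplan-Meier.

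**The concern.** Every included patient has the event, so nobody is censored for time to CR. Slow responders among recent starters are missing from the data altogether. That is right truncation, with a limit equal to the time between the patient's start and 30 October 2018. Kaplan-Meier, log-rank and Cox methods handle censoring but do not correct for this.

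Start date therefore predicts the observed time to CR even when nothing about the patient or treatment does. If a factor is also related to start date, the two associations combine and the factor appears to speed up CR. SAP 7.2.4 says the log-rank analysis will identify the baseline features that go with a shorter time to CR, and that the hazard ratios will help to produce recommendations on therapeutic strategy. A calendar artefact could be read there as a clinical signal.

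**Working it through.** **No figure to reproduce.** The plan gives no power or effect size; Protocol 8.5 says "it is not necessary to make a sample size calculation". For scale, with 90 events and a factor split 50/50, the standard error of the log hazard ratio is 1/√(90 × 0.5 × 0.5) = 0.21.

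**Inputs from the documents.** The window from June 2007 to 30 October 2018 is about 137 months. There are about 90 cases, all events. The median times to CR cited in SAP 2 are 10.1 months (national registry), 12.6 months (hospital series, drug alone) and 18.5 months (same series, drug plus local treatment).

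**Assumptions.** The distribution of time to CR, the pattern of starts over the window, and how a factor's use changes over time. None of these is in the documents.

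**Step 1: how far truncation reaches.** Take a Weibull time to CR with median M and shape 1.5, so F(t) = 1 − exp[−ln 2 × (t/M)^1.5]. A patient starting w months before the cut-off is seen only if t ≤ w. The observable median is then M × [−ln(1 − F(w)/2)/ln 2]^(1/1.5).

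Example with M = 12.6 and w = 12: F = 0.475, half of it is 0.237, −ln(0.763)/ln 2 = 0.391, and 0.391^(2/3) × 12.6 = 6.7 months.

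| Start before cut-off (months) | Observable median, M = 12.6 | Observable median, M = 18.5 |
|---|---|---|
| 12 | 6.7 | 7.1 |
| 24 | 10.7 | 12.5 |
| 36 | 12.2 | 15.9 |
| 48 | 12.5 | 17.5 |
| 60 | 12.6 | 18.2 |

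Most of the distortion lies in the last 2-3 years of starts, or 3-4 years if CR is slow. A longer-tailed distribution extends it further.

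**Step 2: effect on a hazard ratio.** A factor with true HR 1 was simulated. Starts were uniform, late-weighted or early-weighted over 137 months. Time to CR was Weibull with the three medians (shape 1.5, plus shape 1.0 at 12.6 months), and only cases with CR inside the window were kept. The HR came from one sample of 20,000. The false-positive rate at a nominal 5% came from up to 400 samples of 90.

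| How use of the factor changes | Unadjusted HR | False positives |
|---|---|---|
| Constant | 0.98-1.03 | 4-7% |
| Rises 10% to 60% | 1.02-1.16 | 4-12% |
| Rises 0% to 100% | 1.03-1.30 | 5-25% |
| Mostly last 5 years | 1.08-1.47 | 7-44% |
| Mostly last 2 years | 1.20-2.54 | 9-86% |

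The upper end for a gradual rise, HR 1.16, is ln 1.16 / 0.21 = 0.7 standard errors, which is why it rarely reaches significance with 90 cases.

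**Step 3: what adjustment achieves.**

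- *Linear start date in the Cox model.* For gradual rises the HR returns to 0.97-1.04, with about 4-8% false positives. For use mostly in the last two years it remains 1.18-1.91.
- *Bands for the last three years before cut-off.* In that last case the HR becomes 0.93-1.05. When use is mostly in the last five years and CR is slow or long-tailed, up to 1.17 remains, because some truncation lies outside the bands.
- *Linear term plus a knot at 2016.* This was tested under uniform starts with exponential or lognormal times. For a share rising from 5% to 50-80%, the HR was 0.99-1.07 with 3-5% false positives. For a share of 50-80% only in the last two years, it was 0.96-1.05 with 3-6%.

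**The case against.** **The study is exploratory.** No hypothesis is set and the hazard ratios are presented as measures of association. That limits the harm, but SAP 7.2.4 still sets a 5% significance level through SAP 3.2 and links the results to recommendations.

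**The size depends on assumptions.** This stands. With exponential times, a 10.1-month median and a share rising from 5% to 65%, uniform starts gave an unadjusted HR of 1.38 with 18% false positives; starts declining over the window gave 1.11 with 5%. The 18.5-month median belongs only to the drug-plus-local group, 28 of 64 cases in the cited series. Exponential tails also fit that series poorly: at a median of 12.6 months, exp(−ln 2 × 28/12.6) = 21% of cases would exceed the reported maximum of 28 months.

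**The recommendations concern patients already in CR.** Outcomes after CR are their natural basis, so the link from a biased hazard ratio for speed of CR to a recommendation is less direct than it first looks.

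**Stronger readings a reader might infer, which the documents do not support:**

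- *That a newer regimen will look better.* SAP 7.2.2 lists 4/2 and 2/1 regimens, but nothing says either is newer or that its use rose. The example is hypothetical.
- *That the log-rank tests mislead about regimen.* Regimen and type of treatment enter only the Cox model. The log-rank list covers baseline features.
- *That local techniques get biased hazard ratios.* Techniques are only tabulated. The Cox covariate is type of treatment, meaning sunitinib alone or with local treatment.
- *That PFS is distorted in the same way.* PFS runs from CR and is censored at last follow-up, so the limit on CR date does not truncate it.

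**Conclusion.** The point holds for time to CR. The entry limit right-truncates that outcome by start date, and no planned log-rank or Cox analysis takes start date into account. Baseline factors are exposed through both analyses; regimen and type of treatment are exposed through Cox only.

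The direction is predictable: a factor commoner among late starters is biased toward faster CR. The size is not. It is small for gradual trends or if starts were concentrated early (HR 1.02-1.16 for a 10% to 60% rise). It is large only when use is concentrated in the last 2-3 years of starts (up to 2.54 in the most extreme case). It would be wrong to conclude that every factor whose use rose will appear to cause faster CR. These ranges rest on assumed distributions, start patterns and trends in use; only the registry's own data can show which applies.

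This is a cheap improvement worth making before analysis, not a flaw that invalidates the registry's descriptive aims.

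**What to change.** In SAP 7.2.4:

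1. Add sunitinib start date to the Cox model for time to CR in a flexible form, such as a linear term with a knot at 2016 or yearly bands for the last three years before the cut-off. Do not rely on a linear term alone.
2. Stratify the time-to-CR log-rank tests by start period, with narrow bands in the last three years. Broad strata leave truncation within them: in one check, period strata or a linear term reduced the HR from 1.38 only to 1.11-1.15.
3. Tabulate regimen and type of treatment by start period, to show whether the problem arises in these data.
4. Add a sensitivity analysis restricted to starts at least 3-4 years before 30 October 2018.
5. State the truncation as a limitation of the time-to-CR results.

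No change to the PFS model is needed on this ground. The cost is SAP wording, a few degrees of freedom among about 90 events, and fewer cases in the sensitivity analysis. No new data are needed.
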